#### 5.2.2.3 *Intradialytic cardiac arrhythmias*

Intradialytic new onset cardiac arrhythmias including supraventricular tachycardia, bradycardia, atrial fibrillation, ventricular tachycardia, ventricular fibrillation, asystole/pulseless electrical activity will be diagnosed as per American Heart Association.

#### 5.2.2.4 *Rescue net ultrafiltration*

Emergent use of rescue UFNET with rates higher than the assigned treatment arm for more than 3 consecutive hours.

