#### 5.8.3 SAFETY OUTCOMES

1. Intradialytic hypotensive episodes
2. Intradialytic hypertensive episodes
3. Intradialytic new onset cardiac arrhythmias including supraventricular tachycardia, bradycardia, atrial fibrillation, ventricular tachycardia, ventricular fibrillation, and cardiac arrest
4. Emergent use of rescue UFNET with rates higher than the assigned treatment arm
5. Severe hypophosphatemia (<0.5 mg/dL)
6. Severe hypokalemia (<3.0 mg/dL)
7. Severe hypocalcemia (<1.90 mg/dL or ionized calcium <0.90 mmol/L)
8. CKRT system downtime due to hemofilter clotting or clogging
9. Discontinuation of UFNET due to hemodynamic instability
10. Inability to close surgical wounds due to edema
11. New organ dysfunction
12. Worsening of systolic or diastolic cardiac function on echocardiogram
13. Worsening of pulmonary edema on chest X Ray and or/or CT scan
14. Worsening of ileus on abdominal X Ray and/or CT scan
15. Bowel ischemia or anastomotic breakdown based on intraoperative findings
16. Pressure ulcerations
17. New wound infections
18. New arterial or venous thrombosis
19. Severe anemia requiring red cell transfusions
20. Severe thrombocytopenia requiring platelet transfusions
21. New secondary infections

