#### 7.4.6 RESCUE PROCEDURES

Our goal is to respect clinician autonomy and protect patient safety, while preserving separation of treatment between arms. Thus, we will encourage higher  $UF_{NET}$  rates beyond that which is specified by the protocol at the discretion of treating physician for emergent treatment of refractory hypoxia due to fluid overload or patient requiring massive volume infusion that requires control of fluid overload in the opinion of treating clinician (Table 5). However, following the resolution of emergency indication for fluid overload,  $UF_{NET}$  rate will be resumed as per protocol as determined by the attending nephrologist/intensivist. Being a feasibility randomized trial, the use of rescue rates of  $UF_{NET}$  will be collected as secondary outcomes and will not constitute a protocol violation.

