**Table 5: Criteria for rapid rescue net ultrafiltration**

1.	Severe pulmonary edema with $\text{PaO}_2/\text{FiO}_2 < 150$ and $\text{PEEP} > 5 \text{ cm H}_2\text{O}$ due to fluid overload
2.	Respiratory distress due to fluid overload
3.	Ongoing hourly volume infusion at a rate higher than the assigned treatment group for more than 6 hours
4.	Inability to close surgical wounds due to tissue edema
5.	Failing spontaneous breathing trial due to fluid overload at the discretion of attending intensivist

$\text{PaO}_2$ , partial pressure of oxygen;  $\text{FiO}_2$ , the fraction of inspired oxygen;  $\text{PEEP}$ , positive end-expiratory pressure.

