#### Reference measurements (Daily)

The following parameters will be measured and recorded between 4:00 A.M. and 10:00 A.M. using the values closest to 8:00 A.M. on the days specified in the Time-Events schedule. The following conditions will be ensured prior to measurements: no CKRT changes in the previous 30 minutes, no invasive procedures or ventilator changes for 30 minutes. All vascular pressures will be zero-referenced to the mid-axillary line.

1. If receiving CKRT: CKRT mode, blood flow rate, actual rate, replacement and dialysate flow rate, ultrafiltration rate, UFNET rate, effluent flow rate.
2. If receiving positive pressure ventilation set tidal volume, FiO2, PEEP, and plateau pressures.
3. PaO2, PaCO2, pH, and SpO2
4. Rescue procedures used
  - a. Rescue UFNET rates used beyond the assigned treatment arm
  - b. Vasopressors used for hypotension including dose
  - c. Fluid bolus used for hypotension including volume
5. Serum electrolytes
6. Administration of the following fluids and medication
  - a. Enteral or intravenous corticosteroids
  - b. Intravenous vasopressors
7. Was CKRT interrupted? (YES/NO)
8. Cardiovascular SOFA score
9. Fluid intake and output

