## 13 SAFETY MONITORING

### 13.1 ADVERSE EVENTS

A clinical trial adverse event (AE) is defined as any untoward medical event temporally associated with the use of drug or study procedure in humans, whether or not it is considered related to a study intervention or study procedure. Assuring patient safety is an essential component of this protocol and the Principal Investigators have the primary responsibility for the safety of the individual participants. Thus, the Principal Investigators

will monitor for all AEs from study enrollment until ICU discharge or day 28, whichever occurs first.

Following study enrollment, AEs occurring after the patient received the study interventions will be evaluated at the two clinical sites by the Principal Investigators. Investigators will assess if there is a reasonable possibility that the study procedure caused the event, based on the criteria outlined in [Appendix G1](#).

If a patient's study treatment is discontinued because of an AE, the study investigator must report the circumstances and data leading to discontinuation of treatment in the AE case report forms. AEs will be considered related or possibly related to study treatment only up to 24 hours following discontinuation of CKRT. AEs occurring after discontinuation of CKRT and after transition to IHD will not be considered related to study interventions.

Investigators will also consider if the event is unanticipated or unexplained given the patient's clinical course, previous medical conditions, and concomitant medications as outlined in [Appendix G2](#). An adverse event is considered "unanticipated" if it is not listed in the study protocol (21 CFR 312.32(a)).

The following adverse events will be collected in the case report forms:

- Serious adverse events
- Non-serious adverse events that are considered by the investigator to be related to study intervention or study procedures or of uncertain relationship ([Appendix G](#))
- New onset hypotensive and hypertensive episodes, cardiac arrhythmias, considered by the investigator to be related to rate of fluid removal during CKRT, or of uncertain relationship
- Emergent use of rescue UFNET rates with rates higher than the assigned treatment arm
- Severe hypophosphatemia, hypokalemia, hypocalcemia
- CKRT system clotting, clogging, downtime, and discontinuation of fluid removal due to patient instability.
- Inability to close surgical wounds due to edema

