#### 3.5.3 SAFETY OUTCOMES

1. No. of intradialytic hypotensive episodes
2. No. of intradialytic hypertensive episodes
3. No. of intradialytic new onset cardiac arrhythmias including supraventricular tachycardia, bradycardia, atrial fibrillation, ventricular tachycardia, ventricular fibrillation, and cardiac arrest
4. No. of participants with emergent use of rescue  $UF_{NET}$  with rates higher than the assigned treatment arm
5. No. of participants with severe hypophosphatemia ( $<0.5$  mg/dL)
6. No. of participants with severe hypokalemia ( $<3.0$  mg/dL)
7. No. of participants with severe hypocalcemia ( $<1.90$  mg/dL or ionized calcium  $<0.90$  mmol/L)
8. No. of episodes of stopping CKRT due to filter clotting or clogging
9. No. of participants with discontinuation of  $UF_{NET}$  due to hemodynamic instability
10. No. of participants in whom surgical wounds are left open due to edema
11. No. of participants with new organ dysfunction
12. No. of participants with worsening of systolic or diastolic cardiac function on echocardiogram
13. No. of participants with worsening of pulmonary edema on chest X Ray and/or CT scan
14. No. of participants with worsening of ileus on abdominal X Ray and/or CT scan
15. No. of participants with bowel ischemia or anastomotic breakdown based on intraoperative findings
16. No. of participants with pressure ulcerations
17. No. of participants with new wound infections
18. No. of participants with new arterial or venous thrombosis
19. No. of participants with severe anemia requiring red cell transfusions

20. No. of participants with severe thrombocytopenia requiring platelet transfusions
21. No. of participants with new secondary infections

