### 5.2.2 OTHER VARIABLES

We will use following criteria to adjudicate safety outcomes from intervention initiation to 12 hours following discontinuation of CRKT.

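### SAP 5.2.2.4 counts rescue ultrafiltration only when it lasts more than 3 consecutive hours and gives no reason, while the protocol and the SAP's own outcome list set no minimum duration

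*SAP*

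**What the plan says.** Three places list the outcome without a duration:

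- Protocol 5.8.3, item 4 (repeated in the Section 4 trial summary): emergent rescue "with rates higher than the assigned treatment arm".
- Protocol 13.1, among the adverse events collected on case report forms: emergent use of rescue "rates with rates higher than the assigned treatment arm".
- SAP 3.5.3, item 4: "No. of participants with emergent use of rescue" ultrafiltration. SAP Appendix A makes this a binary safety variable, tested between arms by a Wald test from the mixed model.

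The data capture sets no duration either. Protocol 8.3.2 has a yes/no rescue field in each arm, and the daily reference measurements record rescue "rates used beyond the assigned treatment arm".

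The duration appears only in SAP Appendix B. Section 5.2.2 opens with "We will use following criteria to adjudicate safety outcomes", and 5.2.2.4 then defines rescue as emergent use "with rates higher than the assigned treatment arm for more than 3 consecutive hours". No rationale is attached.

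**The concern.** Rescue is a relevant safety signal in this trial. Protocol 11.1 says that worsening oxygenation under the restrictive strategy may lead to more use of rescue procedures. A reader of the outcome lists would expect the table to show how many patients needed rescue in each arm. Under 5.2.2.4 it shows how many needed rescue for longer than three hours at a stretch.

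Short rescues are plausible under the protocol's own rules. Section 7.4.6 returns the patient to the assigned rate "following the resolution of emergency indication for fluid overload", so a rescue that works quickly should be brief. A rescue of three hours or less also leaves no trace in the deviation count: 7.4.6 says rescue is not a violation, and a deviation needs more than six consecutive hours out of range.

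**Working it through.** The plan gives no figure to reproduce, so the check compares definitions.

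**1. Which text governs the analysis.** SAP Section 2 says Appendix B holds the definitions of derived variables, and 5.2.2 says its criteria adjudicate the safety outcomes. So 5.2.2.4 decides who counts, not the one-line label in 3.5.3.

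**2. What the rule does to one patient.** Take a patient whose only emergent rescue lasts exactly three hours. The labels in protocol 5.8.3 and 13.1 and SAP 3.5.3 cover this patient. SAP 5.2.2.4 does not, since three hours is not more than three. The patient is scored no in the Appendix A test and is absent from both the patient and the episode columns of Table 3.

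**3. Direction.** In one arm with n patients, let R be those with any emergent rescue and S those whose rescues all last three hours or less. The adjudicated count is R − S, with 0 ≤ S ≤ R, so it can equal or fall below the listed count but never exceed it. The between-arm difference in proportions becomes

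(R₁/n₁ − R₂/n₂) − (S₁/n₁ − S₂/n₂).

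This moves only if short rescues are unequally common in the two arms, and it could move either way.

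**4. Size.** S cannot be filled in. Neither document gives a rescue frequency or a distribution of durations, so the shortfall lies anywhere between none and all of the rescued patients.

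**5. Whether another passage supplies the reason.** The other hour rules serve different purposes. Six hours defines protocol deviation (protocol 5.8.1, SAP 4.2.2). The item in Table 5 ("Criteria for rapid rescue net ultrafiltration") about infusion lasting more than 6 hours is a trigger for starting rescue. The protocol's argument against over-sensitive criteria (5.8.1) is about deviations.

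**6. Effect on the primary outcomes.** Mean delivered rate is computed from hourly rates and does not use the rescue flag. A rescue of three hours or less is too short to be a deviation under any reading. Recruitment is unrelated. None of the three changes.

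**The case against.** The case on the other side is substantial, and most of it stands.

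- **Definitions belong in Appendix B.** The protocol defers detail to the SAP, and a short label later given an operational definition is normal drafting. Intradialytic hypertension is listed without a duration and acquires one of more than 1 hour in SAP 5.2.2.2, also unexplained. A reader might infer that 5.2.2.4 contradicts the protocol. It does not: the lists are silent on duration and nowhere say that any duration counts.
- **A persistence rule has a rationale here, even though none is written.** Delivered rate is net of fluids infused in the same hour (SAP 5.2.1.1). In the protocol 7.1 example (70 kg, 100 mL/h infusion, machine at 205 mL/h), suppose the infusion stops and the setting is not changed at once. The net rate is then 205/70 ≈ 2.9 mL/kg/h against a cap of 1.5, with no decision to rescue. Staff are also unblinded.
- **Safety oversight is intact.** A reader might infer that short rescues escape monitoring. Protocol 13.3.2 has the DSMB review rescue frequency by group, and nothing ties that review to SAP 5.2.2.4. The uses are still recorded on the case report form.
- **No bias toward either arm is shown.** A reader might infer that the threshold flatters the restrictive arm. The documents give no rescue durations by arm, so this is unsupported.

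These points answer any claim that the threshold is wrong. They do not answer the remaining one: the final table will not show the outcome as listed, and no reason is given.

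**Conclusion.** The point holds as a minor one. SAP 5.2.2.4 narrows a listed safety outcome without explanation, and the planned row can only undercount emergent rescue relative to the listed outcome. The consequence is one row among 21 safety outcomes, in a trial that protocol 11.3 says is not powered for adverse-event differences. The number of patients affected is unknown and could be zero.

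The textual comparison is certain. That the narrowing will matter in practice rests on an assumption: that some patients have only short rescues. Protocol 7.4.6 makes this plausible, but no figure in the documents establishes it. The change is optional, though worthwhile at its price.

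**What to change.** In SAP 5.2.2.4 and shell Table 3, report two rows by arm:

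1. Participants, and episodes, with any emergent rescue use, taken from the yes/no rescue field in protocol 8.3.2. This matches the listed outcome. The daily rescue record can support the episode count.
2. Rescue lasting more than 3 consecutive hours, as now defined.

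Two conditions should stay out of the any-use row. Do not require a Table 5 indication. Protocol 11.4 also allows faster removal for hypertension and arrhythmias due to fluid overload, which Table 5 omits, and 8.3.2 lists no field for the reason for rescue. Do not define rescue from an hourly rate alone, for the infusion reason given above.

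The cost is one sentence and one added row, with the yes/no field and hourly rates already collected. The downside is that brief uses labelled by unblinded staff enter the first row. The second row lets readers see how far the result depends on them.

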#### *5.2.2.5 Severe hypokalemia, hypophosphatemia and hypocalcemia*

Severe hypophosphatemia will be defined as intradialytic phosphate level  $<0.5$  mg/dL. Severe hypokalemia is defined as a intradialytic potassium level  $<3.0$  mg/dL. Severe hypocalcemia will be defined as intradialytic serum calcium level  $<1.90$  mg/dL or ionized calcium  $<0.90$  mmol/L.

#### *5.2.2.6 Inability to close post-operative surgical wound due to edema*

This will be determined as per the primary surgical service. Abdominal wounds left open for a second look or for abdominal re-exploration should not be counted unless there is concurrent tissue edema precluding abdominal closure.

#### *5.2.2.7 New organ dysfunction due to fluid overload*

New and worsening organ dysfunction will be assessed based on SOFA scoring. For instance, a patient with CV SOFA score of 3 at study initiation and now has score of 4 will be counted as worsening CV dysfunction. We will also capture new diastolic/systolic dysfunction on echocardiogram, pulmonary edema on chest X ray/CT scan, ileus on abdominal X ray/CT scan, bowel ischemia and anastomotic breakdown on CT scan/OR, transaminitis or hyperbilirubinemia; delirium using delirium scores on medical records, poor wound healing, wound infection, and pressure ulceration per nursing records, new onset arterial and venous thrombosis as documented by imaging and clinical examination, and anemia, hemolysis and thrombocytopenia as documented in the laboratory studies.

#### *5.2.2.8 Secondary infections*

New onset secondary infections occurring after initiation of study intervention will be collected based on culture data, antibiotic use and suspected sepsis as per clinician judgment.

## 5.3 APPENDIX C: SHELL TABLES

### 5.3.1 TABLE 1: CHARACTERISTICS OF PATIENTS AT BASELINE

	Characteristics	No. (%)		Unadjusted P value
		Restrictive (N= XX)	Liberal (N=XX)	
Age, years, median (IQR)				
Female sex				
Ethnicity				
White				
Black				
Hispanic				
Asian				
Native Hawaiian				
American Indian				
Other				
Prefer not to answer				
Actual body weight at hospital admission, Kilograms, median (IQR)				
Baseline serum creatinine, mg/dL, median (IQR)				
Estimated glomerular filtration rate, mL/min/1.73m  median (IQR)				
Elixhauser Comorbidity Index score				
Pre-existing conditions				
Hypertension				
Diabetes mellitus				
Chronic kidney disease				
Coronary artery disease				
Heart failure				
Liver disease				
Metastatic cancer				
Chronic pulmonary disease				
Primary diagnosis				
Cardiovascular				
Pulmonary				
Gastrointestinal				
Toxicology				
Infection or sepsis				
Neurologic				
Oncologic				
Other				
Etiology of acute kidney injury				
Sepsis				

	Characteristics	No. (%)		Unadjusted P value
		Restrictive (N= XX)	Liberal (N=XX)	
	Ischemic			
	Nephrotoxic			
	Multifactorial			
	Risk factors for fluid overload in the past week			
	Sepsis			
	Hemorrhage			
	Acute pancreatitis			
	Other			
	Source of admission			
	Home			
	Skilled Nursing Facility			
	Assisted Living Facility			
	Other			
	Admission category			
	Medical			
	Scheduled surgery			
	Emergency surgery			
	Clinical condition at study enrollment			
	Sepsis			
	APACHE-III score, median (IQR)			
	Cardiovascular SOFA score, median (IQR)			
	Vasopressor support			
	Mechanical ventilation			
	Fluid overload percentage			
	Median cumulative fluid balance at study enrollment, median (IQR) mL			
	Median UF rate at study enrollment, (IQR), mL			
	Oliguria/anuria			
	Urinary output, mL/24 hours, median (IQR)			
	Corticosteroid use			

5.3.2 TABLE 2: PRIMARY AND SECONDARY OUTCOMES

	Outcomes	Unadjusted Analysis			Adjusted Analysis		
		Restrictive (N= XX)	Liberal (N=XX)	P value	Restrictive (N= XX)	Liberal (N=XX)	Estimated Effect of Intervention (95% CI)
Primary							
Delivered UF NET rate, mean (SD)							
Delivered UF NET rate, median (IQR)							
No. of participants with protocol deviation							
Recruitment rate per month per site							
Secondary							
Daily fluid balance excluding UF, mL, median (IQR)							
Cumulative fluid balance excluding UF, mL, median (IQR)							
Daily fluid balance including UF volume, mL, median (IQR)							
Cumulative fluid balance including UF volume, mL, median (IQR)							
Duration of kidney replacement therapy, days, median (IQR)							
Duration of mechanical ventilation, days, median (IQR)							
Organ failure free days, days, median (IQR)							
ICU length of stay, days, median (IQR)							
Hospital length of stay, days, median (IQR)							

	Outcomes	Unadjusted Analysis			Adjusted Analysis		
		Restrictive (N= XX)	Liberal (N=XX)	P value	Restrictive (N= XX)	Liberal (N=XX)	Estimated Effect of Intervention (95% CI)
	Kidney replacement therapy dependence at discharge among survivors						
	Hospital mortality						

\$ Adjusted for differences in age, baseline eGFR, APACHE-III score, Elixhauser Comorbidity Index score, mechanical ventilation, admission source, percentage of fluid overload, sepsis, and baseline cardiovascular SOFA score.

[figure not shown]

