## 5 TRIAL DESCRIPTION

### 5.1.1 BACKGROUND

Fluid overload is present in two-thirds of critically ill patients with AKI before initiation of KRT, and despite fluid removal, mortality ranges between 40% to 60%. Emerging evidence suggests that the  $UF_{NET}$  rate, a process of care variable, has a “J” shaped association with mortality (Figure 1). Slower  $UF_{NET}$  rates, compared with faster rates, increase exposure to fluid overload and organ edema. In contrast, faster rates compared with slower rates are associated with hemodynamic instability, hypotension and ischemic organ injury. Thus, both slower and faster rates are associated with mortality compared with moderate  $UF_{NET}$  rates in observational studies (Section 5.2). Thus, it is imperative to determine whether the  $UF_{NET}$  rate-mortality relationship is causal. By establishing the feasibility of the restrictive  $UF_{NET}$  rate group, this proposal will be the harbinger of a phase III trial to examine causal effects of  $UF_{NET}$  rate on patient-centered clinical outcomes.

[figure not shown]
**Figure 1: An emerging conceptual model of the association between  $UF_{NET}$  rate and mortality in critically ill patients.**

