#### 8.3.2 REFERENCE MEASUREMENTS

The following data will provide the basis for assessing protocol compliance and safety as well as between-group differences. Data for each of the variables will be recorded on the days shown in the Time-Events schedule ([Appendix F](#)) until death, discharge from the ICU, or day 28, whichever occurs first. Values will be derived from clinically available data.

1.  $UF_{NET}$  rate
  - a. Restrictive  $UF_{NET}$  rate group
    - i. Time and initial  $UF_{NET}$  rate
    - ii. Time and target  $UF_{NET}$  rate
    - iii. Time and hourly  $UF_{NET}$  rate

- iv. Reason and duration of UFNET hold (if any)
- v. Total volume of UFNET during the study
- vi. Rescue UFNET (YES/NO)
  
- b. Liberal UFNET rate group
  - i. Time and initial UFNET rate
  - ii. Time and target UFNET rate
  - iii. Time and hourly UFNET rate
  - iv. Reason and duration of UFNET hold (if any)
  - v. Total volume of UFNET during the study
  - vi. Rescue UFNET (YES/NO)

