## F. TIME-EVENTS SCHEDULE

### F1. GENERAL DATA COLLECTION

Measurement/Event	Screening	Baseline/ Day 0@	1	2	3	4	5	6	7	8- 14	15- 21	22- 28
Serum Creatinine	X	X	X	X	X	X	X	X	X	X	X	X
Demographics, History and Physical		X										
AKI Cerner alerts	X	X										
Etiology of AKI		X										
APACHE II		X										
Weight*		X	X	X	X	X	X	X	X	X	X	X
Daily FB*		X	X	X	X	X	X	X	X	X	X	X
Restrictive UF NET		X	X	X	X	X	X	X	X	X	X	X
Liberal UF NET		X	X	X	X	X	X	X	X	X	X	X
Ventilator parameters ΦΨ*		X	X	X	X	X	X	X	X	X	X	X
CKRT parameters ΦΨ\$		X	X	X	X	X	X	X	X	X	X	X
ABG*		A	A	A	A	A	A	A	A	A	A	A
Fluids (intake/output)*		X	X	X	X	X	X	X	X	X	X	X
MAP*		X	X	X	X	X	X	X	X	X	X	X
CVP, CI, PPV, SVV, and other hemodynamic data*		A	A	A	A	A	A	A	A	A	A	A
Hypotensive & Hypertensive episodes \$%		X	X	X	X	X	X	X	X	X	X	X
Cardiac arrhythmias \$%		X	X	X	X	X	X	X	X	X	X	X
Use of rescue UF NET rates \$		X	X	X	X	X	X	X	X	X	X	X
Severe hypophosphatemia\$		X	X	X	X	X	X	X	X	X	X	X
Severe hypokalemia\$		X	X	X	X	X	X	X	X	X	X	X
Severe hypocalcemia		X	X	X	X	X	X	X	X	X	X	X
All lab data*		X	X	X	X	X	X	X	X	X	X	X
Vital signs and medications*		X	X	X	X	X	X	X	X	X	X	X
Inability to close surgical wounds		X	X	X	X	X	X	X	X	X	X	X
New organ dysfunction*		X	X	X	X	X	X	X	X	X	X	X
Secondary infections		X	X	X	X	X	X	X	X	X	X	X
SOFA score β*	X	X	X	X	X	X	X	X	X	X	X	X
Vital status		X	X	X	X	X	X	X	X	X	X	X

Measurement/Event	Screening	Baseline/ Day 0@	1	2	3	4	5	6	7	8- 14	15- 21	22- 28
KRT Status		X	X	X	X	X	X	X	X	X	X	X
IHD use			X	X	X	X	X	X	X	X	X	X

X= Required

A=When available

Ψ=Data gathered at times indicated or until 72 hours, whichever occurs first

β=Records clinically available creatinine, platelets, bilirubin, MAP, SBP, FiO2, fluid bolus and vasopressor use

ϕ=Measure during reference period (0600 -1000); other values may be obtained closest to 0800 on the specified calendar date

\* = collected only if the patient is still in the ICU before day 28 and if available in the electronic health records

\$\_= collected only if the patient is on CKRT upto 24 hours following discontinuation of CKRT

%=collected only if the patient is on IHD

@ =Data collected before initiation of study intervention

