### 4.3 ANALYSIS METHODS FOR SECONDARY AND SAFETY OUTCOMES

We will use GLMM regression after adjusting for various prespecified variables. We will consider observed differences between groups to be statistically significant at a two-sided, nominal alpha of 0.05 for all outcomes.

For binary outcomes, we will use the Wald test for GLMM to compare the proportion of patients in the two UFNET rate groups (Appendix A).

For continuous variables, we will report incident rate ratios calculated with zero-truncated negative binomial regression modeling adjusted for prespecified baseline covariates.

For independence from KRT and hospital mortality, we will fit GLMM regression models and report odds ratios with corresponding 95% confidence intervals from logistic regression after adjusting for prespecified baseline covariates. To safeguard against erroneous type I error inflation in secondary outcomes, we will apply the conservative Hochberg procedure for adjustment on multiplicity to two key secondary outcomes of mortality and KRT dependence. Because of the potential for type I error due to multiple comparisons, findings for analyses of the other secondary end points will be interpreted as exploratory.

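### Days on KRT, days ventilated and ICU and hospital stay are compared between arms with no rule for patients who die, so a difference in mortality can look like a difference in duration.

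*SAP*

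**What the plan says.** Four of the nine secondary outcomes are durations. The shell in SAP 5.3.2 (Table 2) lists them as "Duration of kidney replacement therapy, days, median (IQR"), "Duration of mechanical ventilation, days, median (IQR"), "ICU length of stay, days, median (IQR") and "Hospital length of stay, days, median (IQR"). Each row has an unadjusted P value and an adjusted effect with a confidence interval. None is restricted to survivors or to days alive.

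Appendix A of the SAP classes all four as continuous, analysed by GLMM. SAP 4.3 adds: "For continuous variables, we will report incident rate ratios", from a zero-truncated negative binomial model with baseline covariates. No term or rule for death appears.

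SAP section 2 says that Appendix B holds the definitions of all derived variables. Appendix B defines none of these four. It does deal with death elsewhere: 5.2.1.3 counts death before day 28 as dialysis dependent, and 5.2.1.4 credits organ failure free days only while the patient is alive.

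Protocol 8.3.2 collects its reference data "until death, discharge from the ICU, or day 28, whichever occurs first". Protocol 5.1.1 says of this population that "mortality ranges between 40% to 60" percent.

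In protocol Appendix F1 the ventilator and CKRT parameter rows carry a footnote: "Data gathered at times indicated or until 72 hours, whichever occurs first". The columns of those rows, Appendix F2 and section 8.3.2 run to day 28.

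**The concern.** Death ends a course of dialysis, a ventilator course and a stay. If nothing else is specified, a patient who dies early contributes few days, and the comparison cannot tell that from early recovery. Adjustment for baseline covariates does not help, because death happens after allocation.

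The direction matters in this trial. The central hypothesis is that the restrictive strategy leads to fewer complications, death among them. Protocol 5.3.2 and 11.1 list longer KRT and ventilator dependence among its possible harms. If the strategy does lower mortality, its additional survivors accumulate days, and it can appear to prolong dialysis and ventilation. If it raises mortality, a real prolongation can be hidden. The sponsor's earlier renal-recovery analysis, described in protocol 5.2.1, accounted for the competing risk of death. These four outcomes have no equivalent. Protocol 11.7 lists the effect on secondary outcomes among the four things the trial is meant to show.

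**Working it through.** The plan gives no numerical figure for these outcomes, so there is none to reproduce. The check asks how far raw days move when mortality differs and recovery does not.

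**Inputs.** From the documents: mortality of 40% to 60% (protocol 5.1.1, background), an average CKRT course of four days at one site (protocol 5.2.8), a day-28 horizon, and 56 patients per group (protocol 9.1). Assumed: constant hazards, death independent of the end of support, the same support duration in both arms, and underlying median durations of 4, 10 and 20 days.

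**Formulas.** Let a = ln 2 / median be the daily rate at which support ends, and b = −ln(1 − p)/28 the daily death hazard for 28-day mortality p.
- Raw days to end of support, death or day 28: mean = (1 − e^(−28(a+b)))/(a+b); median = ln 2/(a+b).
- Free days with death scored 0: mean = (1 − p) × [28 − (1 − e^(−28a))/a].
- Free days with credit up to death, as SAP 5.2.1.4 does for organ failure: mean = p/b − (mean raw days).

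**Hazards.** p = 40%: b = 0.5108/28 = 0.01824. p = 60%: b = 0.9163/28 = 0.03272.

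**Worked case, median 4 days.** a = 0.6931/4 = 0.17329.
- 40% arm: a + b = 0.19153; mean = (1 − e^(−5.363))/0.19153 = 5.20 days.
- 60% arm: a + b = 0.20601; mean = (1 − e^(−5.768))/0.20601 = 4.84 days.
- Ratio: 4.84/5.20 = 0.93.

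**All cases, 40% v 60% mortality.**

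| Underlying median | Raw mean | Ratio | Raw median | Free days, death = 0 | Free days, credit to death |
|---|---|---|---|---|---|
| 4 d | 5.20 v 4.84 | 0.93 | 3.6 v 3.4 | 13.4 v 8.9 | 16.7 v 13.5 |
| 10 d | 10.44 v 9.24 | 0.89 | 7.9 v 6.8 | 9.4 v 6.3 | 11.5 v 9.1 |
| 20 d | 14.61 v 12.59 | 0.86 | 13.1 v 10.3 | 6.1 v 4.0 | 7.3 v 5.7 |

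Raw days favour the higher-mortality arm in every row. Either free-day rule puts that arm behind.

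**A second set of assumptions.** Support ends at 0.08/day in both arms. Death hazards on KRT are 0.04 and 0.06/day, falling to one fifth after liberation (28-day mortality about 42% v 55%).
- Mean raw days: (1 − e^(−3.36))/0.12 = 8.04 v (1 − e^(−3.92))/0.14 = 7.00, so the higher-mortality arm is 13% shorter.
- KRT-free days with death scored 0: 11.1 v 9.1.

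**Sensitivity of the ratio of means (simulation).**
- 40% v 50% mortality, constant hazard: 0.97 to 0.93.
- 40% v 60%, early deaths (mean 5 days): 0.87 to 0.78.
- 40% v 60%, deaths only on days 14 to 28: 1.00 to 0.96.
- 40% v 60%, survivors' median 4 days and mean 10 days to death: 1.10, a reversal.

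**Size against noise.** For raw days with total rate r, E[X²] = (2/r²)[1 − e^(−28r)(1 + 28r)]. In the second scenario the variances are 117.85 − 8.04² = 53.2 and 92.08 − 7.00² = 43.1. With 56 per group and no allowance for clustering, period or covariates, SE = √((53.2 + 43.1)/56) = 1.31. The shift of 1.04 days is 0.8 SE, about a 12% chance of P < 0.05. With support ending at 0.17/day, the means are 4.75 v 4.34: ratio 0.91, shift 0.4 days, about 0.5 SE.

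**The case against.** The other side has four fair arguments.

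*The direction is not fixed.* A reader might infer that the arm with more deaths will look better. The documents give no timing of death, and the sensitivity results run from a marked shortening to a reversal. They support only that it can look better. A death on day 2 is also not the best possible score: an unventilated patient has zero ventilator days, and a patient liberated on day 1 scores lower.

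*Part of the concern is inferred.* The SAP nowhere says that these durations end at death. That follows from the missing definition together with protocol 8.3.2, which also stops at ICU discharge and so cannot define hospital stay. The 40% to 60% is a background range, not a planning assumption. Protocol 5.3.2 and 11.1 do not call prolonged KRT or ventilation the main harm; they list it with fluid overload, arrhythmia and rescue use.

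*The consequence is limited.* SAP 4.3 treats secondary outcomes other than mortality and KRT dependence as exploratory. Feasibility is judged on separation, deviation and recruitment. The phase III outcomes named in protocol 11.7 are 90-day mortality and KRT dependence. Mortality stands in the same Table 2, and at this sample size the distortion is likely to be within noise.

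*Free days with death scored 0 is only one valid choice.* It differs from the rule in SAP 5.2.1.4, and replacing named outcomes would require protocol edits.

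All four stand as limits on wording, severity and remedy. They do not remove the point: the planned P values and adjusted effects would mix mortality with duration, and reporting mortality in another row does not correct them.

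**Conclusion.** The concern holds in conditional form. Four secondary outcomes are compared between arms as raw days with no death rule, in a population whose cited mortality is high, by a SAP that handles death for two neighbouring outcomes. With no difference in recovery and 40% v 60% mortality under constant, independent hazards, the higher-mortality arm appears about 7% to 14% shorter in mean days and about 0.2 to 2.8 days shorter in median. Early deaths enlarge this; late deaths nearly remove it; longer support of decedents reverses it. The hazards and the mortality split are assumptions. Because the outcomes are exploratory, this is a change that should be made, not a flaw that threatens the primary feasibility results.

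The 72-hour footnote is a separate inconsistency. A reader might infer that it cuts KRT duration short. It does not: the KRT status, IHD use and vital status rows in F1 carry no such mark and run to day 28. It affects the ventilator and CKRT settings rows only.

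**What to change.** 1. Keep the four named outcomes and define each in SAP Appendix B: start, end, gaps, horizon and what happens at death.
2. Base the between-arm comparison of KRT and ventilation on days alive and free of each to day 28. State one death rule and reconcile it with 5.2.1.4. Under the assumptions above, death scored 0 and credit up to death both give the right direction, so either will serve if it is fixed in advance.
3. Compare ICU and hospital stay as time to live discharge with death as a competing event.
4. In Table 2, show raw days for survivors and decedents separately, without a test. Align Appendix A and SAP 4.3 with the new analyses.
5. State a convention for ventilator status after ICU discharge, because F1 collects ventilator data only in the ICU. The SOFA table in SAP Appendix B already has one for post-ICU scores.
6. Separately, reconcile the 72-hour footnote on the ventilator and CKRT parameter rows of F1 with their day-28 columns, Appendix F2 and protocol 8.3.2.

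The cost is SAP wording and one footnote. Vital status and KRT status to day 28 are already scheduled, and the protocol's outcome list need not change. The downside is that free-day scores mix mortality with duration; the survivor and decedent rows let a reader see which is at work.
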